2.5. ILS Program Description

All four facilities will receive the same ILS Program. Each facility will participate for a total of 18 months, including a 6-month start-up/planning period, a 6 month implementation period, and a 6 month data collection period. Residents eligible for the ILS Program will be identified during the 6-month implementation period, and each resident will be followed for up to 6 months.

The ILS Program has three main components (**Section 6** provides additional detail):

1. Automated identification of NH residents at high risk for injurious falls. Our IT personnel will work with the IT Departments at each of the 4 NH facilities in order to program the automated calculation of the FRAiL model from the EMR/MDS repository. Residents with an estimated FRAiL score $\geq 5\%$ are eligible for the medication review via the IP nurse and videoconferencing. The facility staff may also suggest other residents for participation.
2. The IP nurse will provide recommendations to manage medications. The IP nurse will be supported by an interdisciplinary team including geriatricians, bone health experts, ADRD behavior management experts, nursing, and pharmacist. The IP nurse will develop an Injury Prevention Plan (IPP) with recommendations for medication changes including deprescribing medications association with falls and a prescription for osteoporosis medications. Recommendations will be left for the primary providers to review and co-sign.
3. Virtual case based education sessions to educate staff. We will hold regularly scheduled (up to monthly) virtual case based education with our interdisciplinary team and staff (nurses, CNAs, and providers) from the 4 NH facilities. During the conferences we may review some of the residents from each facility who are at high risk for injurious falls. These sessions could also include educational material on non-pharmacologic strategies to manage dementia with behaviors, falls prevention, deprescribing, and osteoporosis management. Frequency of meetings and content of the meetings will be individualized to each facility needs regarding case review,

education, or other implementation support needs.

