For all eligible patients, The IP nurse will utilize the Medication Algorithm and will review the EMR and additionally available medical records in order to make informed recommendations regarding medication changes. The IP nurse will be supported by an interdisciplinary team (IDT) including geriatricians, bone health experts, dementia behavior management experts, nursing, and pharmacist. The IP nurse will discuss any recommendations with direct care staff as well as residents or proxies. The Injury Prevention Nurse will provide the resident and/or proxy with evidenced based literature, existing decision aid tools, and/or short videos so as to facilitate shared decision making. Using input from the IDT, direct care staff, residents and proxies, the IP nurse will then use the Injury Prevention Plan template to document recommended medication changes including deprescribing medications association with falls and a prescription for osteoporosis medications. Recommendations will be left for the primary providers to review, modify if desired, and co-sign. The IP Nurse will complete an Injury Prevention Service Consultation note summarizing communication with resident, family, NH PRIDE team, facility staff, and prescribers about recommendations for medication changes.

The IP nurse will offer feedback on prescribing practices. We will create monthly feedback forms for each provider to illustrate adherence with medication recommendations. The IP nurse will review these reports with the site champion. We will work with the site champion to employ other methods to maintain engagement specific to each site, such as publically displayed “thermometers” to document aggregate adherence. The IP nurse will also work with the site champion to ensure that staff are communicating any potential adverse events from deprescribing or osteoporosis medications as a result of the study recommendations.

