10. STATISTICAL CONSIDERATION

This is a pilot study to test design and test implementation of the ILS Program in four nursing home facilities. We will largely use descriptive statistics to present our results, and to inform the sample size calculation for a future pragmatic RCT. The following statistical considerations will be considered:

- Qualitative Study (Aim 1) - Using NVivo software, investigators will identify themes and touch points described by participants in an open coding process. Short audio clips may be created to illustrate each theme and re-organized into *ethnography of the fall prevention experience*, with audio clips preserving the family and staff voices.⁴² A similar process will occur to analyze the post-implementation interviews from staff and proxies, in order to identify themes surrounding implementation barriers.

In addition, the team will use process *flow mapping* techniques to describe each step, however minor, necessary to 1) program the automatic calculation of injury risk using the FRAiL model, 2) deprescribe psychoactive and cardiometabolic medications associated with falls and injury, 3) prescribe osteoporosis treatment to reduce injury risk in the setting of a fall, and 4) introduce other best practices to prevent injurious falls in the NH.

- ILS Implementation (Aim 2) - Quantitative measures of acceptability, demand, fidelity, and practicality as defined in **Table 1** will be described using descriptive statistics. As is standard in pilot studies, our sample size target is based on the expected proportion of high-risk residents in the 4 pilot facilities and no statistical testing is planned, thus, formal power calculation was not conducted. However, our goal is to achieve 50% adherence with suggested medication changes, and our sample of 80 residents is sufficient to demonstrate this with a 95% Confidence Interval of +/- 5% [95% CI assuming SD 10% is 47.8-52.2%; assuming SD 20% is 45.6-54.5%]. We will refine the ILS Program until >50% acceptance of ILS recommendations is achieved, using the targets set in Table 1.

Following current recommendations, we will not power the future pragmatic trial on the results of this small implementation study with unstable efficacy estimates, but rather we will use our clinical knowledge and results of previously published trials of deprescribing in order to inform the sample size calculation.⁴³

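### Section 10's +/-5% precision assumes 80 independent residents; at the plan's SD of 20% it is lost if the home-level ICC exceeds about 0.015

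*Combined protocol and SAP*

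**What the plan says.** Section 10 (ILS Implementation, Aim 2) sets the target: "our goal is to achieve 50% adherence with suggested medication changes". It then claims that "our sample of 80 residents is sufficient to demonstrate this with a 95% Confidence Interval of +/- 5" percent and supports this with two intervals: "95% CI assuming SD 10% is 47.8-52.2%; assuming SD 20% is 45.6-54.5" percent. The same paragraph says that "no statistical testing is planned, thus, formal power calculation was not conducted", so this is a precision statement and not a power calculation. It gives no ICC, design effect, cluster size or cluster-adjusted interval, and neither does any other section.

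Other sections describe how adherence comes about:

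- Section 4: the residents live in four homes, two near Durham and two near Boston.
- Section 2.5: "Recommendations will be left for the primary providers to review and co-sign".
- Section 6.2: "We will create monthly feedback forms for each provider to illustrate adherence with medication recommendations". Sites may also display their aggregate adherence.
- Section 6.1: each home names one or more champions, whose tasks include tailoring the program locally and promoting uptake of the nurse's recommendations.
- Sections 2.5 and 6.2: the content and frequency of the education sessions are adapted to each facility.

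**The concern.** The program acts on adherence through homes and their providers. Residents of one home share a champion structure, a tailored education program, feedback to staff and, to an unknown extent, the same prescribers. Their adherence is therefore likely to be correlated, and a standard error of SD/sqrt(80) is then too small.

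This is separate from the choice of SD, because a design effect multiplies whichever variance is used. It matters because this is the only precision figure in the plan, and it is offered as support for 80 residents. It also stands next to the intention to keep refining the program until acceptance is above 50%. How far an observed figure can be told apart from 50% depends on the true width of this interval. One or two unusually high- or low-accepting homes could move the pooled figure across the target, and Section 10 does not call for results by home.

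**Working it through.** **Inputs from the protocol.** n = 80 residents, centre 50%, SD 10% or 20%, 95% two-sided (Section 10); four homes (Section 4), so m = 80/4 = 20 residents per home on average.

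**Inputs assumed.** The ICC and the number of residents per prescriber, neither of which is given. Equal cluster sizes are also assumed.

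**Step 1: reproduce the plan's figures.** Half-width = c x SD/sqrt(80).

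- SD 10%, normal: 1.960 x 10/8.944 = 2.19, so 47.8 to 52.2. With t on 79 df (c = 1.990): 2.23, so 47.8 to 52.2.
- SD 20%, normal: 4.38, so 45.6 to 54.4. With t(79): 4.45, so 45.5 to 54.5.

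These match the stated intervals to within 0.1 point. The plan's figures therefore rest on a design effect of 1.

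**Step 2: find how much clustering the +/-5 can absorb.** With DE = 1 + (m - 1) x ICC, the half-width is multiplied by sqrt(DE). Setting it equal to 5 at SD 20%:

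- t(79): DE = (5/4.451)^2 = 1.262, so ICC = 0.262/19 = 0.014.
- Normal: DE = (5/4.383)^2 = 1.302, so ICC = 0.302/19 = 0.016.

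At SD 10% the break-even DE is 5.05 (t) or 5.21 (normal), which gives an ICC of 4.05/19 = 0.21 or 4.21/19 = 0.22.

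**Step 3: half-widths at SD 20%, 20 residents per home.**

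| Assumed ICC | DE | Effective n | Half-width, normal | Half-width, t(79) |
|---|---|---|---|---|
| 0 | 1.00 | 80.0 | 4.38 | 4.45 |
| 0.01 | 1.19 | 67.2 | 4.78 | 4.86 |
| 0.02 | 1.38 | 58.0 | 5.15 | 5.23 |
| 0.05 | 1.95 | 41.0 | 6.12 | 6.22 |
| 0.10 | 2.90 | 27.6 | 7.46 | 7.58 |
| 0.20 | 4.80 | 16.7 | 9.60 | 9.75 |

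At SD 10% the t(79) half-widths for ICC 0.05, 0.10 and 0.20 are 3.11, 3.79 and 4.88, all within 5.

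**Step 4: prescriber as the cluster, for illustration only.** At SD 20% with t(79), the break-even ICC is 0.262/9 = 0.029 for 10 residents per prescriber and 0.262/4 = 0.066 for 5. Both caseloads are assumptions.

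**The case against.** The strongest reply is that this is a descriptive pilot. No test is planned, 80 is the expected number of eligible residents, and a wider interval would change neither the sample size nor a stated decision rule. Section 10 does not promise a pooled confidence interval in the report either. That limits the consequence, but it does not rescue the figure: the plan chose to justify its sample by an interval, and the interval assumes independence.

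Several stronger readings are tempting, and the protocol does not support them.

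- *The +/-5% fails outright.* It fails only above an ICC that the protocol does not give. At SD 20% it survives an ICC of 0.01 by home, and at SD 10% it survives up to about 0.21.
- *A few prescribers each decide for many residents.* Prescriber numbers are not stated. Section 7.2 still has administrators being asked how their medical staff is organised, and Table 2 in Section 6 gives residents and families a say by telephone. That resident-level variation would tend to lower the ICC. Prescriber is also not among the resident data elements in Section 7.3.
- *With four homes the interval is far wider still.* A t multiplier on 3 df (3.18) gives +/-7.1 at SD 20% even with an ICC of 0, and +/-9.9 at 0.05. Much of that comes from having four homes and from treating them as a sample of homes. If the target is adherence in these four homes only, between-home variance need not enter.
- *The future trial loses an ICC that it needs.* Section 10 says that trial will not be powered on this pilot. An ICC for acceptance is not one for injurious falls, and four homes would estimate it poorly.

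A further objection is that the SDs themselves may not apply. The primary provider-acceptance measure in Section 2.4 is yes/no per resident. At 50% its SD is 50 points and the half-width is 1.96 x 50/8.944 = 11.0 without any clustering. That is a separate and larger problem for that measure. Clustering would widen that interval too.

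**Conclusion.** The point holds in conditional form. The +/-5% in Section 10 rests on 80 independent residents, an assumption that is unstated and that sits badly with a program delivered through four homes. At SD 20% there is room for only 26-30% variance inflation, so the flat statement is lost if the home-level ICC exceeds about 0.015. Assumed ICCs of 0.02, 0.05 and 0.10 give about +/-5.2, +/-6.1 to 6.2 and +/-7.5 to 7.6. The statement stands at an ICC of 0.01, and at SD 10% with a normal or t(79) multiplier up to about 0.21.

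These sizes rest on the plan's SDs, on 20 residents in each home and on ICCs that are assumptions. Prescriber-level clustering could matter as well, but it cannot be sized from the protocol. This is a correction to a precision statement in a descriptive pilot, worth making because it costs so little.

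**What to change.** 1. In Section 10, withdraw the flat +/-5%. Restate the precision with a design effect for home over a stated range of assumed ICCs (for example 0.01 to 0.10), for both SDs, and say that the ICCs are assumptions.
2. Report acceptance and adherence by home alongside the pooled figures.
3. If a pooled 95% interval is reported, allow for home as the cluster, and note that four homes make both the ICC and the interval imprecise. State whether the interval refers to these four homes or to homes more widely.
4. Optional: record the prescriber for each resident and examine prescriber-level variation; report the acceptance ICC with the same caveat.

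The cost is a short rewording of Section 10 and a few lines of analysis code. Items 1 to 3 need no extra residents or data collection, because the home is known for every resident. The downside is a wider stated interval.

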2.3. Study Design

This protocol describes refinement and pilot testing activities for the Injury Liaison Service outlined above. The following study designs will be employed:

- 1. Qualitative interviews** will be conducted with approximately 10 NH staff (i.e., nurse, certified nurse aide (CNA), physician, and nurse practitioner who have been employed in a nursing facility for at least 3 months) to gain a better understanding of effective and non-effective injury prevention strategies. Information from these interviews will be used to refine the program during co-design meetings with key stakeholders
- 2. A non-randomized pilot program in four nursing home facilities** will provide data on the implementation of the ILS Program. This includes cross-sectional measures of acceptability, demand, practicality, and feasibility obtained from the electronic medical record (EMR), the IP nurse, and a **post intervention survey** with approximately 60 staff across the four facilities. A **pre-post study design** will be employed in order to measure the safety and efficacy of the ILS Program. Safety and efficacy outcomes will be measured at the resident level.

2.4. Outcome measures. The list of measures, data source, and targets are summarized in Table 1 and described in detail below.

Table 1. Proposed Measures of Implementation, Efficacy, Safety, and Validity with Data Source and Target/Goal

Type	Outcomes	Data Source	Target/Goal
Implementation			
Acceptability	Family acceptance of recommendations	IP Nurse Tracking, staff survey	$\geq 50\%$
	Provider acceptance of recommendations		$\geq 50\%$
	Provider satisfaction		$\geq 80\%$
	Staff participation in virtual case based education program		10 staff/NH/mo.
Demand	Proportion eligible for intervention	IP Nurse Tracking	20%
	Proportion of high risk residents with deprescribing recommendations		50%
	Referral rates to virtual cased based education program		15%
Fidelity	Proportion of targeted staff completing intervention checklists	IP Nurse Tracking	90%
	Cost of IP Nurse per resident		\$225

Practicality	NH staff time	IP Nurse Tracking, staff survey, EMR	<2 hour/mo.	Acceptability: (Primary) Number of families that accepted one or more medication recommendation/ number of families offered a recommendation; Number of patients where
	High-risk Resident 6-mo attrition (death, leave NH)		<40%	
Fidelity/Safety				
Fidelity	No. of deprescribed medications at 3-6 months	EMR	≥1	
	Osteoporosis medication initiation		70%	

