Safety	Behaviors	MDS	<10% increase	
	Functional Decline			
	Unscheduled medical visits	EMR	≤2/facility	
Validation				
Outcome Measure	Injurious falls	MDS and Chart Review	>90% sensitive, >95% specific	

the provider accepted one or more recommendations / number of patients with a medication recommendation; % of staff that indicated they were satisfied or very satisfied with the ILS; proportion of staff that attended one or more virtual case based education sessions

(Secondary) number of total medication recommendations accepted/ total number of medication recommendations; proportion of staff that attended two or more virtual cased based education sessions.

Demand: We will use the FRAiL model to identify residents at greatest risk of injurious falls who are eligible for the ILS Program. Residents with an estimated 2-year risk of hip fracture of ≥5%, or similar target, will be considered high risk and eligible for the program. The facility staff will also be able to refer other at risk patients for participation in the program. Other demand outcomes include the proportion of high risk residents with one or more deprescribing recommendations or with a recommendation for osteoporosis treatment, AND referral rates to virtual case based education sessions, defined as the proportion of high risk residents discussed in these sessions.

Fidelity: At each facility, we will identify targeted staff including nurses and medical providers (physicians, nurse practitioners, or physician assistants) who will be asked to complete the program checklists. Our primary measure of fidelity will be the proportion of staff that complete ≥ 75% of requested checklists. As a secondary fidelity measure we will examine the proportion of resident checklists completed by a provider.

Practicality: We will estimate cost by monitoring the amount of time the IP nurse spends on each eligible resident. Other outcomes include the estimated amount of time the staff spend on the ILS service by self-reported survey AND the six-month attrition of eligible residents from the NH facility due to transfer, discharge to community, or death, as determined by the IP nurse from chart review.

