2.6. Sample Size and Population

We anticipate enrolling approximately 10 NH staff and 10 patient/families for an interview on injury prevention.

We anticipate approximately 20% of long-stay residents at the 4 facilities will be eligible for the medication management program (n=80). See **Section 10, Statistical Considerations** for a full explanation of sample size.

We anticipate conducting interviews to assess the acceptability and practicality of the ILS Program on 60 staff members across the four facilities.

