7.3 Resident assessments

Resident data will be collected by the IP nurse. Charts are abstracted at baseline and again at 1 and 4 months after the study recommendations are finalized, to determine if medication recommendations were followed, and if there was any evidence of adverse events. The IP nurse will hold weekly brief telephonic huddles (~10-15 minutes) with direct care staff to determine staff perceptions of the program and to collect critical information on data missing from chart, such as behaviors.

Demographic: (baseline; chart and MDS) age, gender, race, ethnicity, length of NH stay and proxy contact information (for mailing study information and ability to opt out) and relationship to resident.

Medical co-morbidity: (baseline; chart review) All active medical diagnoses.

Medications: (baseline, 1 and 4 months; chart review) All prescribed medications and doses.

Functional status: (baseline, 1-6 months follow-up via MDS) We will categorize functional status using the Katz ADLs at baseline and during followup

Falls, fractures, injurious falls: (baseline, 1 and 4 months; also via MDS and falls log) We will ascertain falls and falls with injury from the 2 MDS assessments during followup, the facility falls log, and also from chart review.

Adverse events – other major acute illnesses: (baseline, 1 and 4 months; MDS and chart review) We will consider the following adverse events due to medication changes: 1) escalating behaviors, worsening depression, or functional decline following psychoactive deprescribing; 2) unplanned medical visits for hypertension, tachycardia, or hyperglycemia for cardiometabolic deprescribing; 3) new gastroesophageal reflux disease or esophagitis following bisphosphonate

prescription. Each facility will provide limited MDS data at baseline and during follow-up in order to characterize the occurrence of these adverse events. Change in depression, behaviors, and functional status will be measured using the MDS assessment closest to and preceding the program implementation and the subsequent MDS assessment.

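### Section 10's ±5% precision is worked out on all 80 eligible residents, but adherence exists only for residents with a recommendation; at SD 20% the claim needs 62 to 64 scored residents

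*Combined protocol and SAP*

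**What the plan says.** Section 10 plans no testing and no power calculation, but it does make a precision claim. It says "our goal is to achieve 50% adherence with suggested medication changes" and that "our sample of 80 residents is sufficient to demonstrate this with a 95% Confidence Interval of +/- 5"%. The supporting figures are "95% CI assuming SD 10% is 47.8-52.2%; assuming SD 20% is 45.6-54.5"%. The same paragraph then makes more than 50% acceptance the condition for ending refinement of the program.

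The 80 come from Section 2.6: "approximately 20% of long-stay residents at the 4 facilities will be eligible for the medication management program (n=80").

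Other sections define who can be scored:

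- Section 2.4 divides provider acceptance by the "number of patients with a medication recommendation", and family acceptance by the families offered one.
- Section 6.3 limits the 1- and 4-month record review to patients whose recommendation has been finalized.
- Section 7.3 abstracts charts at those times "to determine if medication recommendations were followed".
- Section 2.4, Table 1 sets 50% for "Proportion of high risk residents with deprescribing recommendations" and under 40% for "High-risk Resident 6-mo attrition (death, leave NH").

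**The concern.** A resident for whom no change was suggested has no adherence value. A resident who dies or leaves before the chart review may have none either. Section 10 nevertheless puts every eligible resident into the precision calculation and allows for neither loss.

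The stated precision is the only quantitative argument that 80 residents are enough to show the 50% goal, and 50% is also the threshold for ending refinement. If far fewer than 80 are scored, readers will credit the estimate with more precision than it has. Deprescribing is the most exposed result, and it is one of the two care changes in the central hypothesis (Section 2.1).

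**Working it through.** **Inputs.** n = 80 (Sections 2.6 and 10); SD 10% and 20% (Section 10); 50% with a deprescribing recommendation and the 40% six-month attrition ceiling (Section 2.4, Table 1); reviews at 1 and 4 months (Sections 6.3 and 7.3).

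**Formula.** Half-width = c × SD / √n, with c = 1.96 (z) or the 97.5% point of t on n − 1 degrees of freedom.

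**The plan's own figures.** At n = 80 and SD 10%, z gives 47.81 to 52.19 and t gives 47.77 to 52.23. At SD 20%, z gives 45.62 to 54.38 and t gives 45.55 to 54.45. The printed intervals match within rounding, so the arithmetic is right for n = 80.

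**Scored residents needed for ±5 at SD 20%.** (1.96 × 20 / 5)² = 61.5, so 62 by z; by t it is 64. At most 80 − 62 = 18 residents (22.5%) or 80 − 64 = 16 (20%) can be unscored.

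**Scored residents under the plan's figures.** Assume that attrition runs at a constant rate to 40% at six months, that those who leave are not scored, and that the Table 1 targets are met exactly.

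- Any recommendation, given to all 80: 80 × 0.6^(1/6) = 73 at 1 month; 80 × 0.6^(4/6) = 57 at 4 months.
- Deprescribing recommendation: 80 × 0.5 = 40 with no loss; 40 × 0.6^(4/6) = 28 at 4 months.

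| Case | n | SD 10%, z / t | SD 20%, z / t |
|---|---|---|---|
| All eligible, as in Section 10 | 80 | 2.19 / 2.23 | 4.38 / 4.45 |
| All have a recommendation, 1 month | 73 | 2.29 / 2.33 | 4.59 / 4.67 |
| All have a recommendation, 4 months | 57 | 2.60 / 2.65 | 5.19 / 5.31 |
| Deprescribing, no loss | 40 | 3.10 / 3.20 | 6.20 / 6.40 |
| Deprescribing, 4 months | 28 | 3.70 / 3.88 | 7.41 / 7.76 |

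**Between these cases.** If 90% have a recommendation and are read at 1 month, n = 66 and the half-width at SD 20% is 4.83 / 4.92. At 80% it is n = 59 and 5.10 / 5.21.

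**Yes/no measure.** The rows above suit a per-resident adherence percentage with the SD that Section 10 assumes. Section 2.4's provider measure is yes/no per patient. At 50% its half-width is 1.96 × √(0.5 × 0.5 / 80) = 11.0 points, even with all 80 scored.

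**The case against.** The strongest defence is that Section 10 speaks of all suggested changes, not of deprescribing alone. Osteoporosis recommendations count too. The calcium and vitamin D criteria in Appendix 1, Table 2 are broad, and Section 5.2.3 already excludes residents with under six months' life expectancy. Most eligible residents could therefore receive some recommendation. The 40% is a feasibility ceiling at six months, not a forecast. With near-universal recommendations, even the 4-month half-width of 5.2 rounds to 5. Section 10 makes no separate claim for deprescribing, and no sample-size decision turns on the figure.

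Much of this stands. A reader might infer that adherence is scored only in residents still in the home at chart review, and hence that the plan's own numbers defeat ±5% outright. The documents do not support that. No section says that residents who die or transfer are dropped. Section 10 moves from adherence to acceptance, which Table 1 takes from nurse tracking and a staff survey and which need not require presence at a later review. Nor is Table 1's 50% the share with any recommendation.

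The denominator could also be larger than assumed here. The secondary acceptance measure counts recommendations, not residents, and Section 2.6 does not say whether the 80 include staff referrals.

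The defence does not remove the mismatch itself. The claim is attached to a count of eligible residents, the measure is defined on a subset, and the size of that subset is not given.

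**Conclusion.** The concern holds as a limited one. The printed intervals are correct for 80 scored residents, but 80 is the eligible count. At SD 20% the ±5% claim is conditional on no more than about 20 to 22% of the 80 lacking a recommendation or a follow-up value.

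- It holds if nearly all have a recommendation and adherence is read when the recommendation is made or at 1 month.
- It is marginally exceeded at 4 months, but only if attrition reaches the ceiling at a constant rate and leavers are unscored. Both conditions are assumptions.
- It is not met for deprescribing adherence at Table 1's 50%, even without attrition; with both losses the half-width is about 7.4.
- At SD 10% no case in the table passes ±5%, though the printed ±2.2 can widen to 3.9 (t, n = 28).

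The documents give neither the share with any recommendation nor the scoring of deaths and transfers, so no single half-width can be called the right one. Clustering within the four facilities is left aside here, as it is in Section 10.

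**What to change.** In Section 10:

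1. State that the denominator is residents with a medication recommendation. Name the review time that defines adherence, and say how death or transfer before that review is scored. Table 1 dates the deprescribing count at 3 to 6 months while the text uses 1 and 4 months, so the review time needs settling in any case.
2. Replace the single n = 80 statement with half-widths over a range of scored n, for example 80, 73, 57, 40 and 28, and label the attrition pattern as an assumption.
3. Limit the ±5% claim at SD 20% to 62 to 64 or more scored residents.
4. Report each adherence result with its actual denominator and 95% CI. Use a binomial interval for the yes/no per-patient measure, and do not present the SD-based half-widths as applying to it.

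The cost is wording and a less favourable stated precision: roughly ±4.4 to ±7.8 at SD 20% across those denominators. No extra residents or data collection are needed.
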